10. CONDUCT OF THE STUDY

10.1. STUDY SCHEDULE

- Start of inclusions: January 2017

- Duration of inclusion period: 18 months

- Duration of participation of each patient: 3 days

- Total study duration: 24 months

10.2. SUMMARY TABLE OF FOLLOW-UP

	Pre-inclusion M-6 / M-3	Inclusion D0	Visit D0-D1-D2
Eligibility criteria	X	X	
Collection of informed consent		X	
Medical consultation and clinical examination Weight Height HC Waist/hip circumference SBP, DBP, HR			X
5 ml blood sample during the general biological test carried out for follow-up			X
Evaluations: - VINELAND-II assessment scale - CBCL questionnaire - BSID III - Evaluation of eating behaviour - Evaluation of orality - MRI - Oculometry			X
Collection of AEs and SAEs			X

10.3. PRE-INCLUSION VISIT

The pre-inclusion visit is performed by the investigator during a follow-up hospitalization or by telephone ahead of a planned hospital stay at the reference centre. The patient information sheet will be sent to the family by email or by post.

During this pre-inclusion visit, the investigating doctor will present the study to the parents (or legal representative). The presentation of the study will take place at the latest 90 days prior to the inclusion visit to explain the objective of the research, the nature of the constraints, foreseeable risks and the expected

outcomes of the research. The doctor will also outline the rights of the patient and his/her parents (or legal representative) in the framework of biomedical research and will check the eligibility criteria. The parents (or legal representative) will then have time to read the project, contact the investigator if necessary and will be entirely free to give a positive or negative response. After this information session, the parents (or legal representative) have a reflection period of 2 to 10 days.

The investigating doctor is responsible for obtaining the written informed consent from the parents (or legal representative) of the patient. The consent form will be signed by at least one parent (or by the legal representative) at the latest by D0 at the inclusion visit, before any clinical or paraclinical examination is carried out as part of the research.

The various copies of the information leaflet and consent form signed by the parent(s) will then be distributed as follows:

- a copy of the information leaflet and signed consent form is given to the patient and his/her parents.
- another copy is kept by the investigating doctor in a safe place inaccessible to third parties.

10.4. INCLUSION VISIT (D0)

The inclusion visit will be carried out under the responsibility of an investigating doctor of the study at the Hospital of Toulouse during a 3-day hospital stay planned for the normal follow-up of the patient. It will be verified that the information on the set-up and objectives of the research has been understood correctly.

During this visit, the investigator will ensure that the consent form has been signed by the parent(s) (or the legal representative) and the eligibility criteria will be checked.

10.5. FOLLOW-UP VISIT D0 - D1 - D2

The assessments planned for the study are spread over the 3 days of the hospital stay (D0, D1, D2) in the paediatric endocrinology department of Hôpital Pierre-Paul Riquet / the Children's Hospital where the child is admitted.

- A clinical examination is carried out in order to record the weight, head circumference and waist/hip circumference. Blood pressure and heart rate are measured.
- During the fasting blood test carried out for the usual follow-up of the patient, an additional 5 ml tube is taken to measure the circulating rates of ghrelin and certain peptides and neuropeptides involved in regulation of the appetite.
- The psychologist administers the Vineland-II questionnaire in consultation with the parents, as well as the eating behaviour questionnaire (approx. 1.5 hours). He/she will collect and if necessary complete the CBCL questionnaire with the parents.
- The speech therapist will administer the "language" scale of BSID III to the child (approx. 1 hour).
- The psycho-motor therapist will administer the "motor skills" and "cognition" scale of BSID III to the child (approx. 1 hour).
- A midday meal is filmed in order to assess eating behaviour.
- A radioscopy of the swallowing process (15 mins + installation time) and a recording of the voice are made by the speech and language pathologist. Depending on availability, these examinations will be carried out

either in the radiology department of the Children's Hospital or in the ENT department on the site of Hôpital Larrey. In the latter case, the patient and his/her parents will be transported by a hospital ambulance.

At the Brain and Cognition Research Centre, in Baudot ward on the Purpan site, the assessments will include:

- an fMRI (30 minutes + installation time)
- oculometric tests using eye-tracking (30 minutes).

10.6. STOPPING RULES FOR THE STUDY

Withdrawal from the study may take place:

- ✓ by the considered decision of the parents or legal representative,
- ✓ or by necessity, after a decision by the investigator, in the event of the occurrence of an unacceptable adverse event.

10.7. CONSTRAINTS LINKED TO THE STUDY AND POSSIBLE INDEMNIFICATION OF THE SUBJECTS/PATIENTS

The main burden for the patient is to undergo additional assessments during their routine 3-day hospital stay at CHU de Toulouse, in particular clinical tests, a videofluoroscopy, a medical imagery examination and an additional 5 ml blood sample.

It is important to state that these examinations form part of the standard examinations carried out at the reference centre on children with PWS.

The person must not be included in another interventional biomedical study for the duration of the study. There is no subsequent exclusion period.

10.8. COLLECTION OF BIOLOGICAL SAMPLES

A plasma bank will be set up in order to additionally measure hormonal levels of ghrelin and certain peptides and neuropeptides involved in regulation of the appetite (leptin, cortisol, insulin, GLP-1, PYY, pancreatic polypeptide, orexin A, αMSH).

During the fasting blood test carried out for the normal follow-up of the patient, an additional EDTA tube of 5 ml will therefore be taken. The tubes will be centrifuged, the plasma collected and aliquoted then stored at -80°C before measurement. The samples will be coded using a code including the acronym of the study (OT2suite) and the identifying number of the patient specific to the research (cf. 14.3).

The plasma bank will be kept at -80°C at the Biological Resources Centre (CRB) of CHU de Toulouse under the responsibility of the principal investigator, [name]. At the end of the study, the collection will be kept for 10 years in order to be able at a later date to make hormonal level measurements not accessible at the time of the study.

11. MANAGEMENT OF ADVERSE EVENTS AND NEW FACTS

11.1. DEFINITIONS

Adverse event (article R. 1123-39 of the Public Health Code)

OT2SUITE V1.6 of 22/03/2017

Any detrimental event occurring in a person taking part in biomedical research, whether or not this event is linked to the research or to the product being studied.

Adverse reaction (article R. 1123-39 of the Public Health Code)

Any unwanted event due to the research.

Serious adverse event or reaction (article R. 1123-39 of the Public Health Code and ICH guideline E2B)

Any unwanted event or reaction which:

results in death,

endangers the life of the person participating in the research,

requires admission to hospital or a longer stay in hospital,

causes a significant or persistent incapacity or handicap,

is a congenital anomaly or birth defect,

or any event considered to be medically serious (according to the medical judgement of the investigator), and regarding the medicine, regardless of the dose administered.

Unexpected adverse reaction (article R.1123-39 of the Public Health Code)

For research involving non-medical products such as OT2suite, an unexpected adverse reaction is considered to be any undesirable effect the nature, severity or evolution of which does not correspond to the information relating to the actions taken and methods used during the research. The reference document for assessing the unexpected nature [of the reaction] will be the protocol, in particular paragraph 11.2.

New fact (ruling of 24 May 2006)

New safety information, liable to lead to a re-evaluation of the risk/benefit ratio of the study, or which could be sufficient to consider modifying documents relating to the study, the conduct of the study, or if applicable, to the use of the product.

11.2. DESCRIPTION OF THE EXPECTED SERIOUS ADVERSE REACTIONS

- - linked to the radioscopy of the swallowing process: no reaction expected at the low level of radiation received $(20\mu G)$.
- - linked to the MRI: if the contraindications are respected, no serious adverse reaction is expected for the fMRI study, given that no contrast agent is injected and this method is non-invasive and does not use ionising radiation.
- - linked to the oculometric tests (eye-tracking): no serious adverse reaction is expected with the eye-tracking system, a non-ionising and non-invasive technique. The infra-red light emitted by the eye tracker (TOBI) is not harmful to the human eye.
- - linked to the blood samples: apart from exceptional complications (infection, inflammation, pain at the puncture site), no serious reaction is expected.

These examinations form part of the standard examinations carried out at the reference centre on children with PWS.

Any serious adverse reaction not mentioned in this paragraph will be considered as "unexpected" in this study.

11.3. ACTION TO BE TAKEN IN CASE OF AN ADVERSE EVENT

In the event of the occurrence of an adverse event, whether serious or not, the child will remain hospitalised and will not return home until clinical and biological parameters have returned to normal.

The investigator evaluates the gravity of each adverse event. He must notify the sponsor, without delay from the date on which he is made aware of it, of every serious adverse event or any new fact, if one arises:

- ✓ from the date of signature of the consent form,
- ✓ throughout the patient follow-up provided for by the study,

EVENT TYPE	METHODS OF NOTIFICATION	PERIOD FOR NOTIFYING THE SPONSOR
Non-serious adverse event	In the case report form	No immediate notification
Serious adverse event	Initial SAE declaration form + written report if necessary	Immediate notification of sponsor

Name of pharmacovigilance manager for the sponsor: [name] [name]

CHU de TOULOUSE

[contact] or [name] [contact]

E-mail: [contact]

All these events must be followed-up until complete resolution. Additional information (additional declaration form) concerning the evolution of the event, if not mentioned in the first report, will be sent to the sponsor by the investigator.

The investigator must document the event as fully as possible, giving the medical diagnosis if possible, and establish a causal link between the serious adverse event and the study procedures.

The investigator may transmit, in addition to the SAE declaration form, copies of laboratory results or records of examinations or hospitalisation mentioning the serious adverse event, including relevant negative results, without omitting to anonymize these documents.

If the SAE is not resolved following the initial declaration, the investigator must send the sponsor one or more additional declaration(s) until it is completely resolved (with or without sequelae).

11.4. DECLARATION AND RECORDING OF UNEXPECTED SAES AND NEW FACTS

The sponsor/pharmacovigilance unit will declare the unexpected SAEs and new facts occurring during the research according to the mandatory time limits:

- to the ANSM,
- to the competent Ethics Committee (CPP). The committee will ensure, if necessary, that the subjects participating in the study have been informed of the adverse reactions and that they confirm their consent.

11.5. ANNUAL SAFETY REPORT

Once a year, the sponsor will draw up a safety report comprising:

- the list of serious adverse events likely to be linked to the study, including expected and unexpected serious reactions,
- a concise and critical analysis of the safety of participants in the study.

This report will be sent to ANSM and the CPP within the regulatory time limits.

12. STATISTICAL ASPECTS

12.1. CALCULATING THE STUDY SIZE

The main objective is to compare the communication skills of children with PWS aged between 3 and 4 years who have been treated for 7 days with OT in the OTBB2 study before the 6th month of life with untreated and age-matched children with PWS.

Analysis of the primary outcome measure will be a comparison of the distribution of scores for the Communication domain of Vineland-II:

- Comparison of the means if the hypothesis of normality is verified (graphic verification + description of coefficients of skewness and kurtosis): Student's test and variance comparison test to determine whether the Student's test should take account of unequal variances between the two groups,
- Non-parametric comparison of ranks in the event of non-normal distribution of scores: Mann-Whitney test.

The test of hypotheses which will be carried out in the case of normal distribution of scores for Communication is as follows:

H0: the mean of scores for Communication is identical in the two groups (treated group/control group) $(\mu treated = \mu control)$

H1: the mean of scores for Communication differs between the two groups (μ treated $\neq \mu$ control)

If the p-value in this test is less than 5%, the null hypothesis will be rejected and it will be concluded that there is a significant difference in the Communication scores between the two groups at the threshold of 5%.

Hypotheses for calculating the number of subjects required:

- Bilateral test for comparison of means;

- Expected mean in the control group: this value will be varied: 60, 65, 70, 75, 80, 85 points (estimates of the author of the publication (Dykens et al 2016) concerning children with PWS between 4 and 21 are 79.57 (std. dev = 14.12) on average in group 1 versus 65.05 (std. dev = 17.31) in group 2);
- Standard deviation equal in the two groups and fixed at 15 points;
- Desired power: 80%;
- Significance threshold (α risk): 5%;
- Difference to be shown (clinically relevant): 15 points (i.e. 1 standard deviation);
- Ratio between the size of the two groups (Control Group / Treated Group): this value will be varied: 1 (number of subjects equal in the two groups), 2 (two times more patients in the Control group), 3 (three times more patients in the Control group).

Estimate:

With the STATA 14 SE software, we use the command "power twomeans" in order to estimate the number of subjects required. Estimates are based on the formulae presented by Armitage, Berry and Matthews (2002); Chow, Shao and Wang (2008); and Dixon and Massey (1983)¹.

Moreover, we use the tables proposed by Julious $(2004)^2$ as a basis in the case of a study in parallel groups, for a comparison of means (bilateral test), with a power of 90% and an α risk of 5%.

Results:

To ensure a statistical power of 80% and to show a difference of standard deviation between the scores of the Control group and the Treated group, assuming a mean varying from 60 to 85 in the control group, with an α threshold fixed at 5%, the number of subjects that need to be included would be: 17 patients per group if we include as many patients in the Control group as in the Treated group.

This study will be carried out with the 18 patients included in the preceding OTBB2 study. The number of patients to include in the Control group will be 18 children of the same age.

12.2. STATISTICAL METHODS USED

A statistical analysis plan (SAP) will be defined before the database is frozen. All the statistical analyses detailed in the SAP will be carried out by a statistician from the Methodological Support Unit for Research of CHU de Toulouse using Stata® or SAS® software.

All the study variables will be presented by exposure group (children having received early OT versus children never treated with OT) using the descriptive statistics appropriate to each type of variable.

 Continuous variables: number of non-missing observations, median, 1st and 3rd quartile, minimum and maximum, average and standard deviation.

¹ Armitage, P., G. Berry, and J. N. S. Matthews. 2002. Statistical Methods in Medical Research. 4th ed. Oxford: Blackwell. Chow, S.-C., J. Shao, and H. Wang. 2008. Sample Size Calculations in Clinical Research. 2nd ed. New York: Dekker. Dixon, W. J., and F. J. Massey, Jr. 1983. Introduction to Statistical Analysis. 4th ed. New York: McGraw–Hill.

² Julious, S. A. 2004. Tutorial in biostatistics: Sample sizes for clinical trials with Normal data. Statistics in Medicine; 23:1921-1986.

 Categorical variables: number of non-missing observations, number and percentage of each modality (percentages will be calculated on the basis of the non-missing observations).

Taking into account the limited staff complement, the analyses will primarily be exploratory. For the primary and secondary outcome measures, the total scores and scores per dimension on the different scales (Vineland-II, CBCL, BSIDIII) will be calculated according to the recommendations of the authors. Missing data may be imputed according to the recommendations. The differences in scores obtained in the group of children exposed to treatment before the age of 6 months and the group of control children who have never been treated with oxytocin will be calculated, as well as their confidence intervals at 95%. Comparisons between the exposure groups will be made using a Student's test or a Mann-Whitney test for the scores for the different scales and continuous variables and with a Fisher's exact test for categorical variables. No correction will be applied for the multiplicity of the tests.

For the MRI, the analyses will be made by the MRI team using the same method as that used in the OTBB2 study (article under publication).

All the statistical comparisons on the principal and secondary criteria will be carried out with an alpha risk of 5%.

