- Eligibility criteria:
 - inclusion criteria:
 - infants with PWS (genetic diagnosis confirmed)
 - aged from 3 to 4 years
 - For treated group: infant included in the OTBB2 study
 - For not treated group: infant never treated with OT
 - exclusion criteria: none
- **Arm number or label and arm type**: 2 groups of infants with PWS: infants treated with oxytoxin at the age of 0-6 months and age-matched infants not treated
- **Interventions**: not applicable
- Number of subjects: 18 infants treated with oxytocin at the age of 0-6 months and 18 infants not treated
- **Statistical analysis**: description of variables in the oxytocin treated group and comparison between the treated and the age-matched not treated group by Mann-Witney test for continuous variables and by Fisher's test for nominal variables.
- **Key-words:** Prader-Willi, oxytocin, communication skills, oral skills, brain activity.

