department of CHU de Toulouse, and in particular with [name] who began using this test as part of the routine evaluation and care of her patients. It therefore seems relevant to use the most recent version of this scale. [name] believes that there is no problem using this test at the age of 4 years, even if the upper age limit is 42 months, given that these children have a developmental delay. In order to rate the competences of the child in detail and make qualitative observations, the application of the BSID-III scale will be filmed. The use of video media for rating this test is standard practice.

- o The assessment of eating behaviour, comprising:
 - a questionnaire on eating behaviour (cf. Appendix 4) is designed and used in clinical routine by the psychologist of the PWS Reference Centre in Toulouse. Indeed, no validated scale currently takes into account the eating behaviour problems encountered specifically in children with PWS, particularly at this age. It is completed during the interview with the parents.
 - a filmed assessment of eating behaviour during a meal.
- o The assessment of orality, comprising:
 - a recording of the voice
 - a videofluoroscopy of swallowing, which represents the "gold standard" for the objective assessment of swallowing problems. It will be carried out and interpreted by the speech and language pathologist of the Reference Centre who carries these out routinely. This is a video radioscopy, the recorded images of which can be reviewed and discussed after the examination, by another expert if need be. The contrast medium used for the radioscopy of the swallowing process is Micropaque®, produced by Laboratoire Guerbet (cf. SPC, appendix 5). It is an oral suspension. In the context of the trial, each child will receive 10 ml of Micropaque® diluted in 20 ml of apple juice.
- The cerebral activity, studied by BOLD effect in functional MRI (carried out at INSERM U825 in Baudot ward, Purpan Hospital under the responsibility of [name], the head of this unit). Two types of acquisition will be carried out: a morphological MRI and a resting-state functional MRI (rs-fMRI). No injection of contrast medium will be administered to the subjects during this examination. The examination will last approximately 20 minutes. This examination has already been carried out during the OTBB2 study on the 18 infants with PWS.

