1 1 1 1 1	2 2 2 2 2 2 2 2 2 2 2 2 2 2 2 2 2 2 2 2	14 14 15 16 16 17 18 18 18 18 18 18 18 18 18 18 18 18 18	Cruel(le) ave Provoquant(e) Ses exigence Immédiateme Détruit ses a Détruit des a d'autres enta A de la diarri (en l'absence Désobélssan Perturbé(e) p Ne veut pas	c les animaux a) as doivent être satisfaites ant flaires personnelles ffaires appartenant à sa famille ou à ants née ou des selles liquides a de maladie) at(e) au tout changement de routine	0 0 0 0 0	1 1 1 1 1	2 2 2 2 2	38. 39. 40. 41. 42.	parents A du mal à s'endormir A des maux de tête (sans cause médicale connue) Tape les autres Retient sa respiration Fait mal aux animaux ou aux gens sans en avoir Fintention A l'air malheureux(se) sans raison évidente				

2001 T. Achenbach & L. Rescorla. Reproduced by permission.
 Adaptation française : C. Capron, Université de Montpellier III, France
 F.C. Verhulst & J. van der Ende, Erasmus MC – Sophia, Nederland
 Adresse : Erasmus MC - Sophia, [name]
 www.aseba.nl

Version 2005-1-5

TOUTE REPRODUCTION SANS AUTORISATION EST INTERDITE

1000			Internalizing	The last	20				Exter	Externalizing	y
2 2 2 2 2 2 2 2 2 2 2 2 2 2 2 2 2 2 2											
8888		-	\	1 \	\langle	14		1 1	•		•
2	Emotionally Renetive	-	Anxions		Somatic		Withdrawn	_	Attention Problems		Aggressive Rehavior
Total Seere		H	-		p.c		**				•
T Score	9.		8	L	7		83	Ц	5.		5
Percentile	200	-	75		2		27		*	- 1	p.
	6 ECONCOMUNE 16,7-edding 16,540 16,54		III-Chap III Indingel ton III Uporthylop 45 LoshColopy IC Footh III Sod		1 Acher Ness 2 Uliverpicke 20 Headsches 26 Stemes 20 Voorsing 50 Voorsing	- + + = = - 0 0 0	2.Astribung 1.Astribung 12.Astribung 12.Astribung 12.StribungAffaz 12.StribungAffaz 12.Stribunga 12.Stribung 13.Stribung 14.Stribung 15.Stribung 16.Villulanna 16.Villulanna		Montenance Monten	. A = - 8 = - 8 8 8 8 8 8 8 8 8 8 8 8 8	14 Creditional (15 Defaul (16 Detaun (16 Detaun (17 Det

ANNEXE 4: ECHELLE D'EVALUATION DU COMPORTEMENT ALIMENTAIRE

- Enfant :

- Evaluation faite par la mère	le p	ère		
	Pas du tout d'accord	Plutôt pas d'accord	Plutôt d'accord	Tout à fait d'accor
 Votre enfant mange de façon excessive (vu son âge) ⇒ depuis quand son appétit est-il augmenté? 				
2. Il est excessivement préoccupé par la nourriture				
3. Il réclame des quantités importantes lorsqu'on le sert				
4. Il met trop de nourriture à la bouche à la fois				
5. Il compare le contenu de son assiette à celui des autres				

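### Section 12.2 and the abstract give Fisher's exact test different scopes and neither provides for ordered categories, such as items 1-13 of the eating-behaviour questionnaire

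*Protocol*

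**What the plan says.** Section 12.2 describes two types of variable, continuous and categorical, and gives two test rules. One is a "Student's test or a Mann-Whitney test for the scores for the different scales and continuous variables". The other is a comparison "with a Fisher's exact test for categorical variables". It also says that "the total scores and scores per dimension on the different scales (Vineland-II, CBCL, BSIDIII) will be calculated according to the recommendations of the authors". The eating-behaviour questionnaire is not in that list.

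The statistical paragraph of the abstract (section 2) pairs Mann-Whitney with continuous variables and compares the rest "by Fisher's test for nominal variables".

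Section 9.2 makes the questionnaire part of the secondary assessment of eating behaviour. It explains that the centre designed the form itself because "no validated scale currently takes into account the eating behaviour problems encountered specifically in children with PWS". The form is reproduced in Annexe 4. Items 1-13, for example "Il est excessivement préoccupé par la nourriture", are each answered on four levels running from complete disagreement to complete agreement. Item 14 asks at what time of day the child is hungriest, and item 15 is an open description. Neither 9.2 nor Annexe 4 defines a total or sub-score.

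**The concern.** The two places set different limits for the same test. Categorical is the wider word and takes in ordered answers. Nominal does not. Under the abstract the ordered items have no test at all. Under 12.2 they are neither continuous nor one of the three scales named for scoring, so the only class left is the one sent to Fisher.

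Fisher's test on a table of two groups by four levels gives the same p-value if the four columns are shuffled. A move from full disagreement to full agreement counts no more than a move between neighbouring levels. A small p-value does not say whether treated children eat better or worse. Section 12.2 promises differences with 95% confidence intervals for scores, so an unscored item would get no directional estimate from that sentence either.

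Orality and eating behaviour is a named secondary objective (section 4.2), and eating behaviour is among the effects the synopsis hopes to show. With 18 children per group there is little power to give away.

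**Working it through.** **Inputs from the protocol.** 18 children per group (12.1); alpha 5% for all criteria (12.2); two-sided testing (12.1); a difference of 15 points with SD 15, that is 1 SD, for the primary outcome (12.1). The protocol gives no expected effect and no answer distribution for the questionnaire. The 1 SD shift is therefore borrowed from the primary outcome, and the answer distributions below are assumptions.

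**The plan's own figure.** For a two-sided t test with a difference of 1 SD, noncentral-t power is 78.1% at 16 per group, 80.7% at 17 and 83.0% at 18. The stated 17 per group is reproduced. No power is stated for the questionnaire.

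**Model for one item.** Control probabilities fix cut points c_k = Φ⁻¹(cumulative proportion up to level k). Treated cumulative proportions are Φ(c_k − δ), with δ = ±1 or ±0.5. Since items 1-13 describe problem behaviour, a benefit is a downward shift (δ < 0). For controls 25/25/25/25 and δ = −1, the treated cumulative proportions are Φ(0.326) = 0.628, Φ(1) = 0.841 and Φ(1.674) = 0.953.

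**Tests.** Let a_k and b_k be the treated and control counts at level k, with m_k = a_k + b_k.
- Given the margins, P(table) = Π C(m_k, a_k) / C(36, 18). Fisher's p is the sum of P over all tables no more probable than the observed one.
- Midrank r_k = Σ_{j<k} m_j + (m_k + 1)/2; W = Σ a_k r_k; E(W) = 18 × 37/2 = 333. The exact Mann-Whitney p is the sum of P over tables with |W − 333| at least as large as observed.
- The tie-corrected normal version uses Var(W) = (18 × 18/12) × [37 − Σ(m_k³ − m_k)/(36 × 35)].

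Power is the total multinomial probability of all outcomes with p ≤ 0.05. Each group has C(21, 3) = 1,330 possible outcomes, and all 1,330 × 1,330 pairs were enumerated, so there is no simulation error.

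**Results at 1 SD, 18 per group**

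| Control split (%) | Shift | Fisher | Mann-Whitney exact | Gain, exact | Mann-Whitney tie-corrected |
|---|---|---|---|---|---|
| 25/25/25/25 | either | 56.6% | 73.5% | 16.9 | 74.7% |
| 40/30/20/10 | down | 50.1% | 66.2% | 16.1 | 69.1% |
| 10/20/30/40 | down | 59.1% | 76.1% | 16.9 | 77.5% |
| 60/20/15/5 | down | 39.1% | 50.0% | 10.8 | 57.3% |
| 60/20/15/5 | up | 57.3% | 74.0% | 16.8 | 75.3% |
| 40/10/10/40 (polarised) | either | 56.9% | 65.6% | 8.7 | 68.0% |
| 70/20/8/2 (strong floor) | down | 31.9% | 34.9% | 3.0 | 47.7% |

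Upward shifts for 40/30/20/10 and 10/20/30/40 mirror each other's downward rows. Gains are in percentage points, taken before rounding.

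**At 0.5 SD**, Fisher against exact Mann-Whitney:
- 25/25/25/25: 17.0% against 25.8% (gain 8.8).
- 40/30/20/10: 15.6% against 23.4% down (7.8) and 16.9% against 26.0% up (9.1).
- 60/20/15/5: 13.0% against 18.0% down (5.0) and 15.6% against 23.6% up (8.0).

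**False-positive rate.** With no difference and controls at 25/25/25/25, the rates are 4.8% (Fisher), 4.5% (exact Mann-Whitney) and 5.0% (tie-corrected). At 70/20/8/2 they are 4.0%, 3.4% and 5.0%. In these settings the gain is not bought with an inflated error rate.

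**A case the other way.** If one group answers 40/10/10/40 and the other 10/40/40/10, Fisher has 90.4% power and Mann-Whitney 7.5%. Such a difference is in spread, not in direction.

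**The case against.** The strongest reply is that the protocol never assigns these items to Fisher. Annexe 4 is headed "ECHELLE D'EVALUATION DU COMPORTEMENT ALIMENTAIRE", so the form is called a scale, and scale scores go to Student or Mann-Whitney. The three named scales may be named only because their authors published scoring rules, which an in-house form does not have. Read with the abstract, categorical in 12.2 may simply mean nominal. Section 12.2 also announces an SAP, and the scoring of one exploratory questionnaire is a normal thing to leave to it.

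Much of this stands. A reader might infer that the protocol orders Fisher's test for the questionnaire. It does not, and the allocation is only the natural reading while the items remain unscored. A reader might also take the missing total score as a defect, but that can be left to the SAP. What remains is that the protocol states a rule rather than leaving the matter open, that the rule differs between two places, and that the wider version suits ordered data badly. The word for scale in the annex heading supplies no score to test.

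The power figures also have limits. They rest on assumed distributions, they concern single items rather than a sum, and they shrink at a floor. A floor is plausible for items such as eating in secret or hoarding food, since section 3.1.1 places increased interest in food after age 3.

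**Conclusion.** The point holds as a matter of wording with a modest statistical cost. Section 12.2 and the abstract disagree on the scope of Fisher's test, and neither covers ordered categories. If the unscored items 1-13 were tested as 12.2 most naturally reads, each would lose about 11-17 points of power for a 1 SD directional shift with spread or moderately skewed answers. The loss would be mostly 8-9 points at 0.5 SD (5 in the most skewed of these splits), and about 3 against the exact rank test at a strong floor with a downward shift.

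Two stronger conclusions might be drawn, and the documents support neither. The 11-17 points is not a general loss: it depends on assumed distributions, an effect size borrowed from another instrument, and a directional difference. Nor is the whole questionnaire affected: item 14 is nominal, so Fisher suits it, and item 15 is free text. Section 12.2 calls the analyses primarily exploratory, eating behaviour is also assessed from a filmed meal, and the primary analysis of the Vineland-II Communication score is unaffected. The severity is minor.

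**What to change.** In 12.2, restrict Fisher's exact test to nominal and binary variables, which brings it into line with the abstract and still covers item 14. Add that ordered categorical variables, including items 1-13 of Annexe 4, are compared with the Mann-Whitney test, with tie correction or in exact form, and say which. Make the same addition for ordered variables in the abstract.

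A summed score for items 1-13 is optional. If one is wanted, the SAP can define it before the database is frozen and should label it unvalidated. The power figures above do not apply to a sum.

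The cost is one or two sentences, with no extra data, children or assessments. The one trade-off is that a rank test has little power for differences in spread without direction, and such differences would not answer the question of this secondary objective.
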